4.4.3. Method of Assigning Subjects to Treatment Groups (Randomization)

Per International Conference on Harmonisation (ICH) guideline E6: Good Clinical Practice (GCP), screening records were kept at the participating VTEU site to document the reason why an individual was screened, but failed study entry criteria. The reasons why individuals failed screening were recorded in the Statistical and Data Coordinating Center’s (SDCC) AdvantageEDCSM (Electronic Data Capture System).

Once consented and upon entry of demographic data and confirmation of eligibility for this study, the subject was enrolled. Subjects were assigned randomly to 1 of 3 treatment arms (Table 1). The first treatment arm (n=10) was vaccinated with one dose of 15 µg of A/H3N2v HA. The second treatment arm (n=10) was vaccinated with two doses of 3.75 µg of A/H7N9 HA given with AS03 approximately 28 days apart. The

third treatment arm (n=10) was vaccinated with two doses of 3.75 µg of A/H7N9 HA given without AS03 adjuvant approximately 28 days apart. All study vaccinations were administered intramuscularly.

Enrollment of subjects was done online using the enrollment module of AdvantageEDCSM. The randomization code was prepared by statisticians at the SDCC and included in the enrollment module for this study. AdvantageEDCSM assigned each subject to a treatment arm after the demographic and eligibility data had been entered into the system. A designated individual at the participating VTEU site was provided with a code list for emergency unblinding purposes, which was to be kept in a secure place.

4.4.4. Selection of Doses in the Study

As with other avian influenza strains, the immunogenicity of inactivated vaccines is poor. Higher doses of hemagglutinin (HA), a major target of the protective immune response, has been shown to generate more frequent and higher antibody titers. Thus, two doses of 3.75 mcg of HA (A/Shanghai/2/2013) were administered for the A/H7N9 arms. Standard dosing of 15 mcg of HA (A/H3N2v) was chosen to more closely resemble the dosing administered as part of seasonal influenza vaccination. While 15 mcg represents a 4-fold increase in HA amount, the vaccine was unadjuvanted and matches what is formulated in seasonal standard dose inactivated influenza vaccines.

4.4.5. Selection and Timing of Dose for Each Subject

The dose of vaccine was chosen primarily to mirror the amount provided in DMID 10-0074 in which 3.75 mcg of influenza A/H5N1 virus vaccine was given with or without AS03. This reduced amount represents the minimal amount of HA needed to generate an immune response in the presence of an oil-in-water adjuvant system, based on prior studies. The HA content was kept the same for the unadjuvanted dose in an effort to measure the adjuvant effect specifically. Further, in previous studies, two doses of avian-strain influenza vaccine were required to generate an adaptive response, and typically the second dose was given 3-4 weeks after the first dose.

4.4.6. Blinding

This was a partially-blind clinical study as the unadjuvanted A/H3N2v vaccine treatment arm was open-label to avoid the need for placebo administration at approximately Day 29. Investigators and study personnel remained blinded to allocation of A/H7N9 with or without AS03. The randomization scheme was generated by the SDCC and provided to unblinded study personnel (i.e., research pharmacists performing study vaccination preparations and unblinded study vaccine administrators) at the participating VTEU site. The unblinded study vaccine administrator was a study personnel member credentialed to administer vaccines and may also have participated in dose preparation but was not involved in study-related assessments or had subject contact for data collection following study vaccine administration.

4.4.7. Prior and Concomitant Therapy

Administration of any medications, therapies, or vaccines was recorded on the appropriate data collection form. Concomitant medications included all current medications and medications taken within 60 days prior to signing the informed consent form through approximately 28 days after the last study vaccination or through the early termination visit (if prior to 28 days after the last study vaccination), whichever occurred first. Medications reported in the electronic case report form (eCRF) were limited to those taken within 30 days prior to the first study vaccination through approximately 28 days after the last study vaccination. Prescription and over-the-counter drugs were included as well as herbals, vitamins and supplements. In addition, receipt of non-study influenza vaccines was solicited through approximately 28 days after the last

study vaccination and reported in the eCRF. Use of new medication should have prompted evaluation for the presence of a new diagnosis of chronic medical disease or condition. Medications that might interfere with the evaluation of the investigational product(s) should not have been used during the study-reporting period (approximately 12 months after the last study vaccination) unless clinically indicated as part of the subject's health care. Medications in this category included the prohibited medications per the Subject Exclusion Criteria (see Section 4.3). In addition, the site principal investigator or appropriate sub-investigator may identify other medications that should not have been used due to a risk to subject safety or assessment of reactogenicity and immunogenicity.

4.4.8. Treatment Compliance

Study product was administered to subjects by an unblinded study vaccine administrator via intramuscular (IM) injection at all dosing times according to subject treatment assignment and as described in Section 6.2 in the protocol. The number of administered vaccine doses was recorded.

4.5. Immunogenicity and Safety Variables

The following section describes the collection of safety and immunogenicity variables. For a detailed schedule of activities refer to Appendix B of the protocol.

4.5.1. Immunogenicity Variables

Venous blood samples (approximately 10 mL) for HAI and Neut antibody assays were collected from subjects at Day 1 (immediately prior to the first study vaccination), and at approximately Days 29 (for A/H7N9-vaccinated subjects this was collected immediately prior to the second study vaccination) and 57 (A/H7N9-vaccinated subjects only) after the first study vaccination. Subjects who withdrew early had HAI and Neut antibody assays run on available sera, including sera from the early termination visit, if available.

Individual HAI and Neut results will be reported by the central immunology laboratory for the A/Shanghai/02/2013xPR8 vaccine strain and the A/Minnesota/11/2010 vaccine strain for the A/H3N2v study arm. Assay results will be reported as a reciprocal titer with values of $10 \cdot 2^k$, where $k=0, 1, 2$, etc. The lower limit of detection for the HAI and Neut assays is 1:10; values below the limit of detection will be imputed for analysis using one-half the limit of detection ($10/2 = 5$). For analysis, the geometric mean (calculated on natural log scale) of repeated results for each sample will be computed and used as the response for all subsequent calculations. The variation arising from multiple measurements for an individual at a single time point will not be used in subsequent calculations/statistics. See Section 3.3 for definitions of derived variables for the analysis of HAI and Neut data.

Cytokine and chemokine levels in plasma obtained from venous blood samples were quantitatively measured at approximately Days -7, 1, 2, 4, and 8 (A/H3N2v-vaccinated subjects only) and at approximately Days 29, 30, 32, and 36 for A/H7N9-vaccinated subjects only using the Luminex platform. Cytokine and chemokine levels will be reported as concentrations. Values below the plate-specific LOD for each cytokine and chemokine will be imputed using 1/2 LOD.

4.5.2. -Omics Variables

Transcriptome profiling using RNA-Seq was performed on immune cell subsets collected at approximately Days -7, 1, 2, 4, and 8 (A/H3N2v-vaccinated subjects only) and at approximately Days 29, 30, 32, and 36 for A/H7N9-vaccinated subjects only. Total RNA was isolated using standard methods and subjected to ultra-

high-throughput parallel next generation sequencing. Gene expression levels for each gene were estimated based on the number of mapping sequencing reads.

Proteomics profiling was based on shotgun proteomics using multidimensional liquid chromatography coupled with tandem mass spectrometry and performed on immune cell samples collected at approximately Days -7, 1, 2, 4, and 8 (A/H3N2v-vaccinated subjects only) and at approximately Days 29, 30, 32, and 36 for A/H7N9-vaccinated subjects only. Protein abundance levels for each protein were estimated based on the sample peak intensity ratio compared to the sample that was prepared using a pool of all samples.

4.5.3. Safety Variables

Safety assessments included:

1. Study vaccine-related serious adverse events occurring from the time of the first study vaccination through approximately 1 month (A/H3N2v arm) and 12 months (A/H7N9 arms) after the last study vaccination.
2. Solicited Adverse Events – reactogenicity events occurring from the time of each study vaccination through 7 days after each study vaccination:
 - a) Injection site reactions including pruritus (itching), ecchymosis (bruising), erythema (redness), induration (hardness)/swelling, pain, and tenderness.
 - b) Systemic reactions including fever, feverishness (chills/shivering/sweating), fatigue (tiredness), malaise (general unwell feeling), myalgia (body aches/muscular pain exclusive of the injection site), arthralgia (joint pain exclusive of the injection site), headache, and nausea.
3. Unsolicited Adverse Events – study vaccine-related non-serious adverse events occurring from the time of each study vaccination through approximately 28 days after each study vaccination.
4. Medically-Attended Adverse Events including new-onset chronic medical conditions and potentially immune-mediated medical conditions occurring from the time of the first study vaccination through approximately 1 month (A/H3N2v arm) and 12 months (A/H7N9 arms) after the last study vaccination.

5. SAMPLE SIZE CONSIDERATIONS

The sample size is not based on a formal hypothesis. Rather it is based on practical considerations with the goal of gathering enough information to learn more about immune system responses to the vaccine/adjuvant on the molecular level. DMID Protocol 10-0074, entitled: *“A Randomized, Double-Blinded, Controlled, Phase I Study in Healthy Adults to Assess the Safety, Reactogenicity, and Immunogenicity of Intramuscular Subvirion Inactivated Monovalent Influenza A/H5N1 Virus Vaccine Administered With and Without AS03 Adjuvant: Standard & Systems Biology Analyses”*, showed that sample sizes in this range are sufficient to detect key differential signals and carry out systems biology analyses.

6. GENERAL STATISTICAL CONSIDERATIONS

6.1. General Principles

Continuous variables will be summarized using descriptive statistics (n, mean, standard deviation, median, interquartile range (IQR), minimum, and maximum) unless otherwise specified. The frequency and percentages (based on the analysis population size) of observed levels will be reported for all categorical measures. In general, all data will be listed and sorted by study arm and subject, and when appropriate, by study visit number within subject. All summary tables will be structured with a column for each study arm in the following order: Study Arm 1, Study Arm 2, and Study Arm 3.

6.2. Timing of Analyses

The primary CSR will be completed when all primary and secondary endpoint data are available and the data have been cleaned and locked. Any available data from the long-term, tertiary safety follow-up of applicable subjects may also be included. Additional data from the long-term, tertiary safety follow-up of applicable subjects, exploratory correlation analyses, and data from the proteomics portion of the study will be included in one or more addenda to the CSR.

6.3. Analysis Populations

6.3.1. Safety Analysis Population

The Safety Analysis population includes all subjects who received at least one dose of study vaccine.

6.3.2. Intention-to-Treat Analysis (ITT) Population

The intent-to-treat (ITT) population includes all subjects who received at least one dose of study vaccine and contributed both pre- and at least one post-study vaccination blood samples for serological assessment (HAI or Neut antibody assays) for which valid results were reported.

6.3.3. Per protocol (PP) Population

The per protocol (PP) population includes all subjects in the ITT subset with the following exclusions:

- Data from all available visits for subjects found to be ineligible at baseline.
- Data from all visits subsequent to major protocol deviations, such as:
 - Second study vaccination not received,
 - Receipt of non-study licensed live vaccine within 30 days before or after each study vaccination,
 - Receipt of non-study licensed inactivated vaccine within 14 days before or after each study vaccination,
 - Receipt of immunosuppressive therapy (e.g., corticosteroids) within 30 days before or after each study vaccination.
 - Data from any visit that occurs substantially out of window. Substantially out of window is defined as any visit that occurred outside of the pre-defined protocol window except for the following visits for which windows will be redefined as:

- Day 36: +4/-4
- Day 57: +7/-4

6.3.4. The -Omics Analysis Population

The ‘omics analysis population for the -omics (transcriptomics and proteomics) endpoint analyses will include all subjects who received at least one study vaccination and contributed at least one pre- and one post-vaccination sample for ‘omics testing for which valid results were reported. In addition, the following exclusions will be applied:

- post-second dose samples from subjects in Study Arms 2 and 3 that did not receive second vaccination will be excluded.
- samples that were collected substantially out-of-window will be excluded. Substantially out of window is defined as any visit that occurred outside of the pre-defined protocol window except for the following visits for which windows will be redefined as:
 - Day 36: +4/-4
 - Day 57: +7/-4

6.4. Covariates and Subgroups

There is no *a priori* plan to adjust the analyses of safety and immunogenicity for covariates or to report results by subgroups.

6.5. Missing Data

For proteomics data relative protein abundance values will be imputed using the k-nearest neighbors imputation algorithm as implemented in the *impute* R package (See SAP Addendum A for further details). Otherwise, no imputation will be performed for missing values.

6.6. Interim Analyses and Data Monitoring

No interim safety or immunogenicity review was conducted.

6.7. Multicenter Studies

This was a single site study.

6.8. Multiple Comparisons/Multiplicity

No multiple testing adjustments will be carried out for the safety, immunogenicity, and cytokine/chemokine endpoints. For -omics endpoints, the false-discovery rates (FDR) based on the Benjamini-Hochberg procedure as implemented in the R *p.adjust* function will be used to control the false positive rate among significantly differentially expressed genes, proteins, and enriched pathways.

7. STUDY SUBJECTS

7.1. Disposition of Subjects

A flowchart presenting the disposition of study subjects, adapted from the CONSORT statement will be included ([Figure 1](#)). The flowchart will summarize the number of subjects who were eligible, enrolled and randomized, lost to follow-up, and analyzed, by study arm. Screened subjects who were ineligible for enrollment in the study will be presented by inclusion and exclusion criteria ([Table 10](#)). A listing of all subjects that received study product is provided in [Listing 1](#). A listing of subjects who discontinued or terminated early from the study will be tabulated in [Listing 2](#). The disposition of subjects in the study will be tabulated by study arm ([Table 8](#)). This table will show the number of subjects who were screened, enrolled and received the first vaccination, received both vaccinations, completed -omics blood draws, completed follow-up, and were included in the per-protocol analysis population. For each analysis population, a summary of excluded subjects by study arm and time point will be presented as shown in [Table 9](#). A tabular listing of all subjects, visits, and observations excluded from certain analysis populations will be provided as specified in [Listing 5](#).

7.2. Protocol Deviations

A summary of protocol deviations will be presented by the deviation category, type, and study arm in [Table 2](#). This table will provide both the number of subjects and the number of deviations for each category and study arm. All subject-specific protocol deviations and non-subject-specific protocol deviations will be included in [Listing 3](#) and [Listing 4](#), respectively.

8. IMMUNOGENICITY EVALUATION

8.1. Serum Antibody Analysis

All immunogenicity analyses will be conducted for both the ITT and PP analysis populations. For each analysis population (ITT and PP) and serum antibody assay (HAI and Neut), geometric mean titers (GMTs and two-sided 95% confidence interval (CI) based on t-distribution) and percent seroconversion ([n/N (%)] and an exact (Clopper-Pearson) two-sided 95% CI as defined in Section 3.3) will be summarized by study arm and post-vaccination time point (Table 14, Table 15, Table 16, Table 17). GMTs over time will be summarized using time trend plots (Figure 2). Subject-level serum antibody titer responses at Day 29 post-last vaccination for all three study arms will be contrasted using bar plots (Figure 3). Differences between the treatments will be evaluated at Day 29 post-last dose using two-sided t-tests adjusting for unequal variance if necessary using a standard t-test or Welch's t-test (Table 18, Table 19, Table 20, Table 21). The decision on whether to adjust for unequal variance will be based on inspection of variances for the three study arms. Differences in seroconversion rates for Day 29 post-last dose will be assessed using a two-sided Fisher's exact test (Table 22, Table 23, Table 24, Table 25). Data listings of HAI and Neut assay results will be provided in Listing 8 sorted by study group, subject ID, and visit.

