2 BACKGROUND INFORMATION AND SCIENTIFIC RATIONALE

2.1 Background Information

Since its emergence in Southeast Asia in 2013, influenza A/H7N9/Shanghai continues to infect humans and is associated with a high case fatality rate¹. The virus holds significant pandemic potential, since the avian population is rarely symptomatic (making avian disease surveillance difficult), and there is little preexisting immunity to the virus in the human population²; however, its current inability to sustain efficient human-to-human transmission has limited its spread³.

Unfortunately, as with other avian influenza strains, the immunogenicity of inactivated vaccines is poor. Higher doses of hemagglutinin (HA), a major target of the protective immune response, generate more frequent and higher antibody titers⁴; however clinical trials of influenza A/H5N1, influenza A/H7N7, and influenza A/H7N9 vaccines have clearly demonstrated that avian HA's are substantially less immunogenic than seen with seasonal vaccines, even when given in very large doses⁵⁻⁷. For example, in clinical studies of a subvirion inactivated influenza A/H5N1/Vietnam vaccine in healthy adults, two 90 mcg doses of vaccine were required to stimulate an antibody response in just over half (57%) of the recipients⁸. A NIAID sponsored Phase I/II trial studying the safety and immunogenicity of an inactivated influenza A/H7N9 vaccine revealed that even two doses of 90 mcg each were insufficient to generate measurable antibody responses in healthy adults⁹. Moreover, adjuvant was required to induce protective responses against inactivated A/H7N9 vaccine in two NIAID sponsored Phase I clinical trials. While 59% of subjects seroconverted when vaccinated with 3.75 mcg of A/H7N9 vaccine in the presence of MF59 adjuvant, only 5% of subjects seroconverted when vaccinated with 45 mcg of A/H7N9 vaccine in the absence of MF59 adjuvant^{6,7}.

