4. INVESTIGATIONAL PLAN

4.1. Overall Study Design and Plan

This is a single center, randomized, partially-blinded, Phase II, small, targeted, prospective study in approximately 30 healthy male and non-pregnant female subjects aged 18 to 49 years old, inclusive, designed to evaluate and compare the immunogenicity between an intramuscular monovalent inactivated influenza A/H7N9 virus vaccine manufactured by Sanofi Pasteur given with and without AS03 adjuvant manufactured by GlaxoSmithKline, and an intramuscular unadjuvanted monovalent inactivated influenza A/H3N2v virus vaccine manufactured by Sanofi Pasteur.

This study will use a standard and systems biology approach to assess the human early gene and protein signatures expressed at baseline (approximately Days -7 and 1), and at approximately Days 2, 4, and 8 (A/H3N2v-vaccinated subjects only) after the first study vaccination in each treatment arm as well as at approximately Days 29, 30, 32, and 36 in A/H7N9-vaccinated subjects only. Cellular immunogenicity (systems biology studies) data will be integrated with serologic immunogenicity (HAI and Neut antibody assays) and reactogenicity data to develop a systems model of the human immune response to unadjuvanted monovalent inactivated influenza A/H3N2v virus vaccine and monovalent inactivated influenza A/H7N9 virus vaccine given with and without AS03 adjuvant.

This study will use venous blood samples and subject data collected from a total of thirty vaccinated subjects randomly divided into three equal treatment arms (Table 1). The first treatment arm (n=10) will be vaccinated with one dose of 15 µg of A/H3N2v HA. The second treatment arm (n=10) will be vaccinated with two doses of 3.75 µg of A/H7N9 HA given with AS03 approximately 28 days apart. The third treatment arm (n=10) will be vaccinated with two doses of 3.75 µg of A/H7N9 HA given without AS03 adjuvant approximately 28 days apart. All study vaccinations will be administered intramuscularly.

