Table 20: t-Test Results for Comparing Day 29 Post-Last Vaccination Neutralizing Antibody Titer Between Treatment Groups in the Intent-to-Treat Population

Table 21: t-Test Results for Comparing Day 29 Post-Last Vaccination Neutralizing Antibody Titer Between Treatment Groups in the Per-Protocol Population

Table 22: Fisher’s Exact Test Results for Comparing Day 29 Post-Last Vaccination Seroconversion based on Hemagglutination Inhibition Antibody Titer Between Treatment Groups in the Intent-to-Treat Population

	Study Arm 2 A/H7N9 + AS03, D1, 29 (N=X) vs. Study Arm 3 A/H7N9 + PBS, D1, 29 (N=X)	Study Arm 2 A/H7N9 + AS03, D1, 29 (N=X) vs. Study Arm 1 A/H3N2v, D1 (N=X)	Study Arm 3 A/H7N9 + PBS, D1, 29 (N=X) vs. Study Arm 1 A/H3N2v, D1 (N=X)
n	xx	xx	xx
Seroconversion n/N (%) [95% CI]	xx/xx (xx%) [xx, xx]	xx/xx (xx%) [xx, xx]	xx/xx (xx%) [xx, xx]
Exact Odds Ratio(95% CI)	x.xxx	x xxx	x.xxx
p-value	x.xxx	x xxx	x.xxx
N = Number of subjects in the Intent-to-Treat Population n = Number of subjects with available results P-value = two-sided Fisher’s Exact test P-vale.			

Tables with similar format:

Table 23: Fisher’s Exact Test Results for Comparing Day 29 Post-Last Vaccination Seroconversion based on Hemagglutination Inhibition Antibody Titer Between Treatment Groups in the Per-Protocol Population

Table 24: Fisher’s Exact Test Results for Comparing Day 29 Post-Last Vaccination Seroconversion based on Neutralizing Antibody between Treatment Groups in the Intent-to-Treat Population

Table 25: Fisher’s Exact Test Results for Comparing Day 29 Post-Last Vaccination Seroconversion based on Neutralizing Antibody between Treatment Groups in the Per-Protocol Population

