Interferon-gamma	Day 4 (Post-Vaccination 2) vs. Pre-Vaccination 2	n/a	x xxx (x xxx)	x.xxx (x xxx)
Interferon-gamma	Day 8 (Post-Vaccination 2) vs. Pre-Vaccination 2	n/a	x xxx (x xxx)	x.xxx (x xxx)

Colored in blue= p-value < 0.05

Continue for the remaining cytokine/chemokines IL-1b, IL-2, IL-4, IL-5, IL-6, IL-7, IL-8, IL-10, IL-12p70, IL-13, IL-17A, IL-21, IL-23, ITAC, MIP 1a, MIP1b, MIP3a, TNF-alpha, IP-10, IFNa, IFNb

Table with similar format:

Table 123: Wilcoxon Signed-Rank Test Results for Comparing Cytokine/Chemokine Concentrations between Pre- and Post-Vaccination Time Points in the Per-Protocol Population

Table 124: Wilcoxon Rank Sum Test Results for Comparing Fold Changes between Study Groups in the Intent-To-Treat Population

		Study Arm 2 A/H7N9 + AS03, D1, 29 (N=X) vs. Study Arm 3 A/H7N9 + PBS, D1, 29 (N=X)	Study Arm 2 A/H7N9 + AS03, D1, 29 (N=X) vs. Study Arm 1 A/H3N2v, D1 (N=X)	Study Arm 3 A/H7N9 + PBS, D1, 29 (N=X) vs. Study Arm 1 A/H3N2v, D1 (N=X)
Cytokine	Comparison	Wilcoxon Statistic (p-value)	Wilcoxon Statistic (p-value)	Wilcoxon Statistic (p-value)
Fractalkine	Day 2 (Post -Vaccination 1) vs. Pre-Vaccination 1	x xxx (x xxx)	x xxx (x xxx)	x.xxx (x xxx)
Fractalkine	Day 4 (Post-Vaccination 1) vs. Pre-Vaccination 1	x xxx (x xxx)	x xxx (x xxx)	x.xxx (x xxx)
Fractalkine	Day 29 (Post-Vaccination 1) vs. Pre-Vaccination 1	x xxx (x xxx)	n/a	n/a
Fractalkine	Day 2 (Post-Vaccination 2) vs. Pre-Vaccination 2	x xxx (x xxx)	n/a	n/a
Fractalkine	Day 4 (Post-Vaccination 2) vs. Pre-Vaccination 2	x xxx (x xxx)	n/a	n/a
Fractalkine	Day 8 (Post-Vaccination 2) vs. Pre-Vaccination 2	x xxx (x xxx)	n/a	n/a
GM-CSF	Day 2 (Post -Vaccination 1) vs. Pre-Vaccination 1	x xxx (x xxx)	x xxx (x xxx)	x.xxx (x xxx)
GM-CSF	Day 4 (Post-Vaccination 1) vs. Pre-Vaccination 1	x xxx (x xxx)	x xxx (x xxx)	x.xxx (x xxx)
GM-CSF	Day 29 (Post-Vaccination 1) vs. Pre-Vaccination 1	x xxx (x xxx)	n/a	n/a
GM-CSF	Day 2 (Post-Vaccination 2) vs. Pre-Vaccination 2	x xxx (x xxx)	n/a	n/a
GM-CSF	Day 4 (Post-Vaccination 2) vs. Pre-Vaccination 2	x xxx (x xxx)	n/a	n/a
GM-CSF	Day 8 (Post-Vaccination 2) vs. Pre-Vaccination 2	x xxx (x xxx)	n/a	n/a
Interferon-gamma	Day 2 (Post -Vaccination 1) vs. Pre-Vaccination 1	x xxx (x xxx)	x xxx (x xxx)	x.xxx (x xxx)
Interferon-gamma	Day 4 (Post-Vaccination 1) vs. Pre-Vaccination 1	x xxx (x xxx)	x xxx (x xxx)	x.xxx (x xxx)
Interferon-gamma	Day 29 (Post-Vaccination 1) vs. Pre-Vaccination 1	x xxx (x xxx)	n/a	n/a

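### With 10 per arm, Fisher's test and an odds ratio serve the between-arm seroconversion comparison less well than an unconditional exact test and a rate difference

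*SAP*

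**What the plan says.** SAP 8.1: "Differences in seroconversion rates for Day 29 post-last dose will be assessed using a two-sided" Fisher's exact test. Protocol 11.5.2 names the same test for comparisons between arms.

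The Table 22 shell in SAP Appendix 1 has three pairwise columns, with Arm 2 against Arm 3 first. Its rows are n, seroconversion n/N (%) with a 95% CI, "Exact Odds Ratio(95% CI"), and a p-value. It has no difference in rates and no rule for a zero cell. Tables 23-25 repeat the format for the other population and the other assay.

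The design has "a total of thirty vaccinated subjects randomly divided into three equal treatment arms", that is, 10 per arm. SAP 4.2 calls Arms 2 and 3 the main arms, and learning what AS03 does to the response is the stated goal.

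The primary HAI endpoints (SAP 3.2) are percentages of subjects seroconverting. SAP 8.1 and Table 14 summarise them by arm with Clopper-Pearson intervals.

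**The concern.** Two features of the planned comparison fit poorly with 10 subjects per arm and a low expected response in one of them.

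First, Fisher's test conditions on the total number of responders. With so few subjects its attainable p-values are widely spaced, so its real false-positive rate is far below the nominal level and power is lost. Boschloo's test uses the Fisher p-value as its statistic and calibrates it over the unknown common rate. It keeps the level and never gives a larger p-value.

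Second, Protocol 2.1 describes unadjuvanted H7N9 vaccine as very weakly immunogenic. An arm with 0/10 responders is then a likely result, and it makes the sample odds ratio infinite.

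At stake is how much the Arm 2 against Arm 3 table can say about AS03 and seroconversion, using data the trial will collect anyway.

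**Working it through.** **Inputs**

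- n = 10 per arm: SAP 4.1.
- Two-sided Fisher's test and exact odds ratio: SAP 8.1 and Table 22.
- Level 0.05 two-sided: an assumption. The SAP gives no level for this test; among the immunogenicity tables 0.05 appears only as the cytokine highlight rule ("Colored in blue= p-value < 0.05").
- Rates 59% and 5%: an assumption taken from Protocol 2.1: "While 59% of subjects seroconverted when vaccinated with 3.75 mcg of A/H7N9 vaccine in the presence of MF59 adjuvant", and "only 5% of subjects seroconverted when vaccinated with 45 mcg of A/H7N9 vaccine in the absence of MF59 adjuvant". The first figure is for another adjuvant and the second for a higher dose. Neither document uses them for planning, so a range is shown.

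The documents state no power or size for this comparison, so there is no figure of theirs to reproduce.

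**Fisher p-values.** For x2 responders in Arm 2 and x3 in Arm 3, with m = x2 + x3, the probability given m is C(10,x2)·C(10,x3)/C(20,m). With equal arms the two-sided p is twice the tail.

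- 4/10 vs 0/10: 2 × 210/4845 = 0.087
- 5/10 vs 0/10: 2 × 252/15504 = 0.033
- 6/10 vs 1/10: 2 × (210×10 + 120×1)/77520 = 0.057

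With 0/10 in Arm 3, Arm 2 therefore needs at least 5/10 to reach p ≤ 0.05.

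**Boschloo p-values.** p = max over π of Σ b(i;10,π)·b(j;10,π), summed over all tables (i,j) whose Fisher p is no larger than the observed one. This gives 0.042 for 4/0 and 0.023 for 6/1. Over all 121 possible tables it never exceeds the Fisher p. Six table types (and their mirror images) move below 0.05: 4/0, 6/1, 7/2, 8/3, 9/4 and 10/6.

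**Maximum true size** (rejection probability at a common rate, maximised over that rate): Fisher 1.28%, at a rate of 0.5; Boschloo 4.22%.

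**Power** = Σ b(i;10,p2)·b(j;10,p3) over the rejected tables.

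| Arm 2 / Arm 3 rate | Fisher | Boschloo |
|---|---|---|
| 59% / 5% | 61.3% | 78.1% |
| 50% / 5% | 43.1% | 62.8% |
| 70% / 5% | 80.5% | 91.3% |
| 59% / 10% | 45.5% | 64.1% |
| 59% / 2% | 72.9% | 87.3% |

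At 59%/5% the gain is 78.1 − 61.3 = 16.8 points. Most of it comes from two tables: 4/0, with probability 0.1209 × 0.5987 = 0.072, and 6/1, with 0.2503 × 0.3151 = 0.079.

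**Other evaluable numbers.** Protocol 5.2.4 replaces subjects to secure at least 10 evaluable per A/H7N9 arm, so n may differ from 10. Fisher's maximum size is 2.1% at 9/9, 2.7% at 11/10, 1.7% at 11/11 and 2.3% at 12/12. Power at 59%/5%, Fisher then Boschloo, is 59.0% and 71.1% at 9/9, 71.2% and 78.3% at 11/10, and 69.7% and 79.1% at 11/11. The gain is largest at exactly 10 against 10.

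**Odds ratio.** P(0/10 in Arm 3) = (1 − p3)^10: 0.95^10 = 0.60, 0.90^10 = 0.35, 0.98^10 = 0.82. At a 59% rate Arm 2 is almost never also 0/10 (0.41^10 = 0.0001). In these cases the point estimate and upper limit are infinite. The exact lower limit stays finite: 1.20 for 5/10 vs 0/10 and 1.77 for 6/10 vs 0/10.

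**The case against.** Protocol 11.2 declares the study exploratory, Protocol 11.4.3 and SAP 5 base the sample size on practical considerations, and no significance level is set for this test. No decision hangs on p falling below 0.05, and every power figure above borrows that threshold. This stands, and it limits how much the point matters. It does not remove it: the p-values will still be printed, and Boschloo's is no larger than Fisher's at any threshold.

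Fisher's test is valid and standard. Tables 22-25 contain 12 tests (3 pairs × 2 assays × 2 populations), and SAP 6.8 plans no multiplicity adjustment for immunogenicity. A conservative test is defensible in that setting. This also stands, and it is a real cost of the change.

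A reader might infer that the primary analysis is impaired, because HAI seroconversion is a primary endpoint. The documents do not support that. The primary endpoint is the percentage in each arm, and its Clopper-Pearson interval is defined at 0/10 and 10/10.

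A reader might also infer that the effect cannot be estimated in about 60% of trials under the protocol's own rates. That is too strong. The 5% is a background figure for 45 mcg unadjuvanted vaccine, and the probability runs from 0.35 to 0.82 as the assumed rate moves from 10% to 2%. Only the point estimate and upper limit of the odds ratio are lost. The exact lower limit, the p-value and both arm rates remain, and Tables 18-21 give a GMT ratio with a CI. What is missing is an interval for the difference in seroconversion rates.

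**Conclusion.** The point holds as a cheap gain in efficiency and reporting for the exploratory between-arm comparison, worth considering. It shows no error in the primary endpoint summary, no inflated error rate and no contradiction between the documents.

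At an assumed two-sided 5% level with exactly 10 against 10, Fisher's test uses at most 1.3% of the 5%, and Boschloo's uses 4.2%. That result does not depend on the background rates. The power difference does: 61% against 78% at 59%/5%, and across the other rates checked from 43% against 63% to 81% against 91%. How often the odds ratio is infinite depends almost entirely on the unadjuvanted rate. Protocol 2.1 says higher HA doses give more frequent responses, so a rate at or below 5% with 3.75 mcg is plausible. That would put the probability at 0.60 or higher, but neither document states such a rate.

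**What to change.** In SAP 8.1, Tables 22-25 and Protocol 11.5.2:

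1. Add the difference in seroconversion rates as the main between-arm effect measure, with one named 95% CI method that is defined at 0/10 and 10/10, for example the Miettinen-Nurminen score interval. Keep the exact odds ratio as secondary.
2. Use Boschloo's unconditional exact test and state the convention: the two-sided Fisher p-value as the statistic, maximised over the common rate. The convention must be written down because implementations differ. Another one gives 0.026 for 6/1 and 0.033 for 4/0, against 0.023 and 0.042 here, with the same rejection region at 0.05.
3. Print the Fisher p-value alongside.

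The cost is SAP and protocol wording, a few table rows and standard software; no new data are needed. The downsides are a less familiar test, and a less conservative one across the 12 unadjusted comparisons, although each keeps its 5% level.
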